### 3. SUMMARY

Title	Post-Marketing Clinical Follow-Up trial to evaluate the performance and safety of the medical device PROCTOeze® PLUS in the relief of haemorrhoidal disease and anal irritation symptoms
Study Start Date	28 th October 2024
Study Stop Date	27 th January 2025
Sponsor	BIOKOSMES S.r.l. [name]
Product/medical device description	PROCTOeze® PLUS is a soft and light hydrophilic emulsion, adjuvant for the symptomatic relief of internal and external haemorrhoids and anal irritation. PROCTOeze® PLUS key ingredients are mainly paraffinum liquidum, petrolatum, dimethicone, and hydroxyethyl cellulose.
Intended use	PROCTOeze® PLUS creates a physical barrier that protects the peri-anal tissue, minimizing the possibility of bacterial colonization and contact with local and environmental agents, which may exacerbate haemorrhoid condition. It has a protective, lubricating and refreshing action and emollient properties, which help to prevent irritation and discomfort of the perianal area, providing relief from pain, burning, itching and other related complaints, contributing to the physiological restoration of the anal and perianal tissues. Its application leaves the treated area soft and moisturized, avoiding the onset of irritation and cracking of the skin. The lubricating action helps to facilitate bowel movement, thus minimising the trauma and pain sensation associated with defecation.
Dosage form and Route of Administration	PROCTOeze® PLUS is a soft and light hydrophilic emulsion it is applied, throughout the anal orifice and on the surrounding perianal area to relieve symptoms associated to hemorrhoids and anal irritation, when required up to three/four times per day. To prevent anal irritation and cracking of the skin, it is possible to apply PROCTOeze® PLUS once a day.
Regulatory Status	This product is a substance-based medical device, CE marked, Class IIb rule 21 according to the Regulation (EU) 2017/745
Study Design	Open, non-comparative, multicenters, prospective, interventional trial.
Study Geography and Site Numbers	Three centers in Craiova, Romania
Introduction	Haemorrhoids are present universally in healthy individuals as cushions surrounding the anastomoses between the superior rectal artery and the superior, middle, and inferior rectal veins. Nonetheless, the term "haemorrhoid" is commonly invoked to characterise the pathologic process of symptomatic haemorrhoid disease instead of the normal anatomic structure. Haemorrhoids play a significant physiologic role in protecting the anal sphincter muscles and augment closure of the anal canal during moments of increased abdominal pressure (e.g., coughing, sneezing) to prevent incontinence and contribute 15 to 20% of the resting anal canal pressure. Increases in abdominal pressure increase the pressure in the inferior vena cava that cause these vascular cushions to engorge and prevent leakage. PROCTOeze® PLUS, a soft and light hydrophilic emulsion able to provide symptomatic relief of haemorrhoids and anal irritation thanks to its formulation (s). Moreover, due to its formulation, the product contributes to the physiological restoration of anal and perianal tissues.

Study Rationale/Purpose	The Research Question of the present trial is the following: in a population of adult patients, men and women, suffering from symptomatic haemorrhoids, will the administration for 4 weeks of the IMD PROCTOeze® PLUS improve the haemorrhoidal symptomatology, giving results assessed at the end of the treatment by means of validated questionnaires?
Study Objective	
This trial aims to evaluate the overall performance and safety of the MD PROCTOeze® PLUS in relieving symptomatology of haemorrhoidal disease and anal irritation in adult patients affected by Grade I-II (Goligher classification) haemorrhoids as assessed by the patient and the Investigator at the end of the treatment period.
 
The primary objective is the assessment of performance by the improvement in the quality of life (QoL). Secondary objectives are the assessment of performance by validated scales completed by the Investigator and by the patient at the end of the treatment period.
 
The safety of the MD will be evaluated through AE and ADE incidence assessed by Investigators and reported according to the current legislation.

Study Primary endpoints:	
 
The Short Health Scale for Haemorrhoidal Disease (SHSHD) (Annex 3 “Collected variables” ) (5,16,17) will be used to evaluate the QoL. The questionnaire will be administered by the Investigator to each patient during the study visit, at baseline and on day 30, in PAPI mode (Paper and Pen Interview)
 

Secondary endpoints:	
 
The Haemorrhoid Severity Score (HSS) (Annex 3 “Collected variables” ) (6), a physician-reported outcome, will be completed by Investigator at baseline and day 30, at the end of the treatment with the MD
 
The Haemorrhoidal Disease Symptom Score (HDSS) (Annex 3 “Collected variables”) (5,19) is a patient-reported outcome. The questionnaire will be administered by Investigator to each patient at baseline and on day 30, at the end of the treatment with the MD.
 
Evaluation of AE, SAE, ADE, SADE, ASADE, USADE incidence assessed by Investigator and reported according to the current legislation for the whole study period. Device Deficiencies (DD) will be also evaluated.
 

Study Population	Adult patients affected by Grade I-II (Goligher classification) haemorrhoids that did not need hospitalization and treated as outpatients (the treatment will be self-administered at home).
Selection criteria	
 
Men and women ≥ 18 years old.
 
Patients diagnosed with Grade I – II symptomatic haemorrhoids (according to Goligher classification) confirmed by clinical and anoscopic or proctoscopic examination performed within 3 months before baseline.
 
Patients able to do self-administration at home of the MD, for 30 days, to treat symptoms of haemorrhoids and anal irritation.
 
Patient free from the following treatments for haemorrhoids for at least 4 weeks: laser treatments for haemorrhoids, steroid or non-steroidal anti-inflammatory drugs, analgesics, any anti-haemorrhoidal treatment, anticoagulants, and antiplatelet agents.
 
Patients able to communicate adequately with the Investigator and understand the trial questionnaire.
 
Patients able to understand and who can provide valid informed consent to the trial.
 

Study sites	
Unități medicale Specializare: Medicină de familie
 
[name]
 
PI C.M.I. [name]
 
PI C.M.I. [name]
 
PI C.M.I. [name]

Executive summary	
This report summarizes the results of the post-marketing clinical investigation conducted in Romania to evaluate the efficacy and safety of PROCTOeze® PLUS in treating hemorrhoidal symptoms and anal irritation. This open-label, non-comparative, prospective study enrolled 50 patients (68% females and 32% males) with Grade I-II hemorrhoids.
 
The primary endpoint was assessed using the Short Health Scale for Hemorrhoidal Disease (SHSDH) to evaluate quality of life, while secondary endpoints were measured via the Hemorrhoidal Disease Symptom Score (HDSS) and Hemorrhoid Severity Score (HSS).
 
Statistically significant reductions (<math>P < 0.0001</math>) were observed for SHSDH, HDSS, and HSS scores from baseline to the end of treatment. Notably, a significant interaction was observed in the HSS between genders. The device demonstrated good tolerability and an acceptable safety profile

Sample Size Calculation and Statistical Methods	
A total of 50 subjects was be enrolled.
 
Simple size estimation was based on the primary endpoint.
 
By employing a one-tailed Wilcoxon signed-rank test for matched pairs at a significant level of 2.5 % and a power of 80 % we derived a sample size of 50 evaluable patients to prove PROCTOeze® PLUS performance.
 
Considering a possible screen failure rate of 10% we require 55 enrollable patients.
 
In addition, 5 patients should account for a possible 10% moderate drop-out rate, so 60 patients should be screened for enrolment in the clinical investigation.
 
Descriptive statistics (mean, standard deviation - SD- median, first and third quartile - Q1-Q3, min-max) have been calculated for quantitative variables.
 
Absolute and percent frequencies have been calculated for qualitative variables.
 
Comparison between gender on quantitative variables normally/symmetrically distributed have been carried out by means of the Student's t test.
 
The change of the total of the SHSDH (primary objective of the study), on the total of the HSS and HDSS (secondary objectives of the study) between baseline and the end of the study has been assessed, according to the protocol, by means of the Wilcoxon signed-rank test.
 
In addition, the change between Visit 1 and Visit 2 of SHSDH, HSS, and HDSS has been modeled between the two genders by means of the repeated measurement ANOVA with gender as a fixed factor between patients, time as a fixed factor within patients and their interaction.
 
The detailed statistical tables and figures are included below.

Discussion	
The findings of this PMCF study confirm that PROCTOeze® PLUS is effective and safe in relieving the symptoms of haemorrhoidal disease and anal irritation. The significant reduction in pain, itching, burning, and swelling highlights the product's efficacy, while the absence of adverse events demonstrates good tolerability.
 
The statistical analyses demonstrate a significant improvement in quality of life and symptom relief.
 
 
• The SHSDH score decreased markedly, indicating enhanced quality of life.
 
• Both the HDSS and HSS scores showed significant reductions, confirming the device's efficacy in alleviating symptom severity.
 
• The significant interaction in the HSS suggests a gender-related difference in response, which may require further study.
 
• Overall, the safety data were reassuring, with no adverse events reported.
 
 
The integrated tables and figures from the statistical analysis clearly support the robustness of these findings.

Results	
Demographics and Baseline Characteristics
 
 
Number of Patients: 50
 
Gender Distribution 68% female, 32% male
 
Mean Age Approximately 50 years (SD 13.90) with no significant difference between genders (see Table 1 ).
 
 
Outcome Assessments
 
SHSHD
 
 
Baseline: 14.04 (SD 7.79)
 
End-of-Treatment: 7.80 (SD 3.69)
 
Mean Reduction: 6.24 points (P < 0.0001) (See Table 5 and Figure 2 for detailed analysis.)
 
 
HDSS
 
 
Baseline: 10.12 (SD 3.60)
 
End-of-Treatment: 7.20 (SD 2.47)
 
Mean Reduction: 2.92 points (P < 0.0001) (See Table 6 and Figure 3 for detailed analysis.)
 
 
HSS
 
 
Baseline: 8.50 (SD 2.11)
 
End-of-Treatment: 6.48 (SD 2.17)
 
Mean Reduction: 2.02 points (P < 0.0001)
 
A significant Visit x Gender interaction was found (P = 0.0272). (See Table 7 and Figure 4 for detailed analysis.)
 
 
Device Usage
 
Patient diaries indicated a mean usage of approximately 34 cream applications over the 14-day monitoring period, with daily consumption remaining relatively consistent and a slight decrease observed in the later study days.
 
Safety
 
No serious adverse events (SAEs) were reported. No, AE was reported.
										
Conclusions	
This post-marketing clinical investigation demonstrates that PROCTOeze® PLUS is effective in improving quality of life and reducing the symptoms associated with hemorrhoidal disease and anal irritation in adult patients with Grade I-II hemorrhoids.
 
The significant reductions in SHSHD, HDSS, and HSS scores (all P < 0.0001), combined with an acceptable safety profile, support the continued clinical use of PROCTOeze® PLUS.
 
Ongoing post-marketing surveillance is recommended to further confirm the long-term safety of the device.
										
Timing	
 
 Approval by National Bioethics Committee for Medicines and Medical Devices	18th October, 2024	
 
 Start of enrolment (FPI)	8th November 2024	
 
 End of enrolment (LPI)	17th December 2024	
 
 End of treatment (LPO)	16th January 2025	
 
 Final Report of trial	03th April 2025	
 
	Approval by National Bioethics Committee for Medicines and Medical Devices	18th October, 2024	Start of enrolment (FPI)	8th November 2024	End of enrolment (LPI)	17th December 2024	End of treatment (LPO)	16th January 2025	Final Report of trial	03th April 2025
Approval by National Bioethics Committee for Medicines and Medical Devices	18th October, 2024										
Start of enrolment (FPI)	8th November 2024										
End of enrolment (LPI)	17th December 2024										
End of treatment (LPO)	16th January 2025										
Final Report of trial	03th April 2025										

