##### safety outcome

- Evaluation of AE, SAE, ADE, SADE, ASADE, USADE incidence assessed by Investigator and reported according to the current legislation for the whole study period. Device Deficiencies (DD) will be also evaluated.

The HS is a physician-reported measurement instrument based on PNR-Bleed classification, that classifies and describes the haemorrhoids based on the four main characteristics of the hemorrhoidal disease i.e., the degree of hemorrhoidal Prolapse (P), Number (N) of the primary hemorrhoidal columns involved, Relation (R) of the haemorrhoidal tissue to the dentate line and the amount of Bleeding (B) from it. All four components in this classification system are graded into five grades ranging from 1 to 5. Grade 1 is the normal anal cushions and Grade 5 is the worst grade in a specific characteristic. HSS is the total score obtained by the sum of the numerical grades of all four characteristics of haemorrhoids in the PNR-Bleed classification. The minimum HSS score is 4 and the maximum score can be 20. The HSS score of a normal person without any signs and symptoms of haemorrhoids is 4. Calculation of the HSS help in the quantification of the haemorrhoidal disease for further reference and is helpful in post-treatment patient follow-up to grade the response to treatment and to assess the effectiveness or failure of any particular treatment regimen for haemorrhoids. It may also be used in predicting and diagnosing the recurrence after any form of treatment for the haemorrhoids.

- The Haemorrhoidal Disease Symptom Score (HDSS) (Annex 3 “Collected variables”) (5,19) is a patient-reported outcome. The questionnaire will be administered by Investigator to each patient at baseline and on day 30, at the end of the treatment with the MD.

The HDSS is a patient-reported measurement instrument. It comprises five items. Symptoms are assessed using the patient-reported frequency of the 5 symptoms, including pain, itching, bleeding, soiling, and prolapse. Patients are instructed to answer based on their experience during the previous period. Each symptom is graded on a 5-point scale (0 = never, 1 = less than once a month, 2 = less than once a week, 3 = 1–6 days per week, 4 = every day or always), giving a total score ranging from 0 to 20.

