### Short Health Scale for Haemorrhoidal Disease (SHSHD)

#### Short Health ScaleHD

*The following questions deal with how your symptoms caused by hemorrhoids affect your daily life (one answer per question).*

1. In your view, how severe are your symptoms caused by hemorrhoids? Please grade your symptoms on a 7-point scale, where 1 is "no symptoms" and 7 is "severe symptoms."

No symptoms

1 	2 	3 	4 	5 	6 	7  Severe symptoms
----------------------------	----------------------------	----------------------------	----------------------------	----------------------------	----------------------------	--

2. Do your symptoms interfere with your daily activities? Please grade your answer on a 7-point scale, where 1 is "not at all" and 7 is "interfere to a very high degree."

Not at all

1 	2 	3 	4 	5 	6 	7  Interfere to a very high degree
----------------------------	----------------------------	----------------------------	----------------------------	----------------------------	----------------------------	--

3. Do your symptoms cause much concern? Please grade your answer on a 7-point scale, where 1 is "no concerns" and 7 is "constant concerns."

No concerns

1 	2 	3 	4 	5 	6 	7  Constant concerns
----------------------------	----------------------------	----------------------------	----------------------------	----------------------------	----------------------------	--

4. How is your general feeling of well-being? Please grade your answer on a 7-point scale, where 1 is "very good" and 7 is "very bad."

Very good

1 	2 	3 	4 	5 	6 	7  Very bad
----------------------------	----------------------------	----------------------------	----------------------------	----------------------------	----------------------------	-------------------------------------

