### Bibliographical references (5,16,17)

### Haemorrhoidal Disease Symptom Score (HDSS)

1. How often do you feel pain from your hemorrhoids?

Never  Less than once a month  Less than once a week  1–6 days per week  Every day (always)

2. How often do you feel itching or discomfort of the anus?

Never  Less than once a month  Less than once a week  1–6 days per week  Every day (always)

3. How often do you bleed when passing stool?

Never  Less than once a month  Less than once a week  1–6 days per week  Every day (always)

4. How often do you soil your underwear (soiling from the anus)?

Never  Less than once a month  Less than once a week  1–6 days per week  Every day (always)

5. How often do you feel a swelling or a prolapsing hemorrhoid?

Never  Less than once a month  Less than once a week  1–6 days per week  Every day (always)

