## 5. PATIENT DIARY

Visit data   .   .

Compilation instruction

Please from tomorrow for 14 days each day fill this diary.

In the first column insert the data, in the column from two to six put a cross at any Proctinus cream application.

If you take any drug note in the other drug column the name of each drug taken

In the general health column insert information if you have any different disease than hemoroides.

In the column note insert any other relevant information.

For any doubt on the diary filling please contact the doctor of this study

Dr. \_\_\_\_\_ contact number \_\_\_\_\_

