## 9. STATISTICAL ANALYSIS

### Statistical Methods

Descriptive statistics (mean, standard deviation - SD- median, first and third quartile -Q1-Q3, min-max) have been calculated for quantitative variables.

Absolute and percent frequencies have been calculated for qualitative variables.

Comparison between gender on quantitative variables normally/symmetrically distributed have been carried out by means of the Student's t test.

The change of the total of the SHSDH (primary objective of the study), on the total of the HSS and HDSS (secondary objectives of the study) between baseline and the end of the study has been assessed, according to the protocol, by means of the Wilcoxon signed-rank test.

In addition, the change between Visit 1 and Visit 2 of SHSDH, HSS, and HDSS has been modeled between the two genders by means of the repeated measurement ANOVA with gender as a fixed factor between patients, time as a fixed factor within patients and their interaction.

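### The Discussion claims significant reductions in four named symptoms, but only scale totals have reported tests and burning is not a named item on any scale

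*Combined protocol and SAP*

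**What the plan says.** In section 3 (Summary), the Discussion says of the trial's findings: "The significant reduction in pain, itching, burning, and swelling", and offers this as evidence of the product's efficacy.

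Statistical Methods in section 9 says what was tested. It opens with "The change of the total of the SHSDH (primary objective of the study" and applies the same Wilcoxon signed-rank test to the HSS and HDSS totals. The sample size and methods row of section 3 says the same. Tables 5 to 7.3 report totals only, overall and by gender.

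The instruments are described in protocol section 3.5.1 and Annex 3:

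- **HDSS:** patient-reported "frequency of the 5 symptoms, including pain, itching, bleeding, soiling, and prolapse". Item 2 reads "How often do you feel itching or discomfort of the anus" and item 5 reads "How often do you feel a swelling or a prolapsing hemorrhoid".
- **SHS-HD:** four global questions, the first being "In your view, how severe are your symptoms caused by hemorrhoids". No symptom is named.
- **HSS:** prolapse, number of columns, relation to the dentate line, and bleeding, all graded by the physician.

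The diary instructions (section 5) ask for the date, cream applications, other drugs, general health and notes. On general health they say: "In the general health column insert information if you have any different disease than hemoroides".

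The intended-use text in section 3 describes the device as "providing relief from pain, burning, itching and other related complaints".

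**The concern.** The sentence is a statistical claim about four separate symptoms. To support it, a reader would expect a result for each one. The report gives results for three composite totals and none for an individual symptom.

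Burning is the weakest of the four, because no scale has an item that names it. It is also one of the symptoms in the intended-use text and on the product labelling. The protocol synopsis says that the manufacturer must present PMCF results to the Notified Body. A reader there could take the Discussion as trial evidence for symptom-specific relief, including relief of a symptom for which the trial had no separate variable.

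**Working it through.** **1. Reproduce the printed tests, to confirm what they are tests of.** The inputs are the mean and SD of the Visit 1 minus Visit 2 difference in Tables 5, 6 and 7, with n = 50. Paired t = mean / (SD / √50). The range allows for rounding of the mean and SD by ±0.005.

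| Scale total | Mean (SD) | t recomputed | Range from rounding | t printed |
|---|---|---|---|---|
| SHS-HD | 6.24 (5.51) | 8.008 | 7.994 to 8.022 | 8.003921 |
| HDSS | 2.92 (2.51) | 8.226 | 8.196 to 8.257 | 8.213142 |
| HSS | 2.02 (1.71) | 8.353 | 8.308 to 8.398 | 8.361742 |

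All three printed values lie within the rounding range, so the printed tests are tests of the totals. The signed-rank statistics need patient-level data and cannot be recomputed here.

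**2. Confidence interval for the HDSS total.** 2.92 ± 2.010 × 2.51/√50 = 2.92 ± 0.71, which gives 2.21 to 3.63, as printed in Table 6.

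**3. Set the claim beside the instruments.**

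| Symptom claimed | Where it was asked | Result reported for it |
|---|---|---|
| Pain | HDSS item 1, on its own | None |
| Itching | HDSS item 2, with discomfort | None |
| Swelling | HDSS item 5, with prolapse | None |
| Burning | No named item on HDSS, SHS-HD or HSS | None |

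**4. What the HDSS total can say about its items.** The five item mean changes must add up to 2.92. An even spread would be 2.92/5 = 0.58 per item, but many other splits give the same total, including ones in which bleeding and soiling account for part of the fall. No item means or SDs are printed, so the total cannot show a significant fall in pain, in itching/discomfort or in swelling/prolapse taken singly.

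**5. The diary.** The diary results (Tables 4 and 4.1) are counts of applications only. The instructions ask for no symptom rating, and the general health column is for diseases other than haemorrhoids.

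**6. A scoring question that bears on any item analysis.** Protocol section 3.5.1 scores each HDSS item 0 to 4, for a total of 0 to 20. Table 6 prints a minimum of 5.00 at both visits, and at Visit 2 the lower quartile is also 5.00. That pattern would fit five items scored from 1, but the report does not say so and it remains an assumption. A constant shift per item would leave the mean fall of 2.92 unchanged, whereas item levels and percentage falls would depend on it.

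**The case against.** The strongest defence is that the fault lies in one clause. The bullets that follow it in the Discussion, and the Executive summary, Results and Conclusions, speak of scale scores. Testing totals was a reasonable analysis. Pain has its own HDSS item, and itching and swelling are each named in one. All of this stands, and it limits the point to a reporting correction. It does not supply a result for any of the four symptoms.

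A reader might infer that burning was never captured at all. The documents do not support that. A patient could count burning as discomfort in HDSS item 2, or let it influence the global severity question of the SHS-HD. The diary has a free-text note column, protocol section 3.7.2.1 calls its list of diary content non-exhaustive, and the diary grid itself is not in the text available here. What can be said is that burning was not separately measured or analysed.

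A reader might also infer that item-level analyses were never run. The documents show only that none is reported. The Index of Tables does not settle this, since it also omits Table 2.1, which is in the report.

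**Conclusion.** The point holds as a mismatch between one efficacy statement and what was tested. The Discussion asserts significance for four symptoms. The report gives no symptom-level result for any of them, and one, burning, has no named item. The supported statement is the fall in the HDSS total: mean 2.92, 95% CI 2.21 to 3.63, P < 0.0001.

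This rests on the instrument wording in Annex 3, the Statistical Methods text and the printed tables. The conclusion about the diary rests on its instructions alone.

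Two stronger readings should be resisted. The documents do not show that pain, itching or swelling failed to improve; they show only that the total cannot say. Nor does the point weaken the three total-score results, which reproduce from the printed summaries.

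**What to change.** In the Discussion in section 3, replace the symptom clause with: *the HDSS total score fell from baseline to Visit 2 (mean 2.92, 95% CI 2.21 to 3.63, P < 0.0001)*. Remove burning.

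If symptom-level statements are wanted, report the HDSS item results for pain, itching/discomfort and swelling/prolapse under those combined labels, and mark them as post hoc. State how the items were scored, and reconcile that with the 0 to 20 range in protocol section 3.5.1 and the minimum of 5 in Table 6.

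The replacement clause uses figures already printed and needs no new data and no protocol change. The optional item results need a short extra analysis of the HDSS item responses, where these were recorded. The price is a narrower efficacy statement, with no trial claim for burning.

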## **2.3. STUDY OBJECTIVES**

This trial aims to evaluate the overall performance and safety of the MD PROCTOeze® PLUS in relieving symptomatology of haemorrhoidal disease and anal irritation in adult patients affected by Grade I-II (Goligher classification) haemorrhoids as assessed by the patient and the Investigator at the end of the treatment period.

The primary objective is the assessment of performance by the improvement in the quality of life (QoL). Secondary objectives are the assessment of performance by validated scales completed by the Investigator and by the patient at the end of the treatment period.

The safety of the MD will be evaluated through AE and ADE incidence assessed by Investigators and reported according to the current legislation.

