### 3.3.1. Inclusion criteria

Patients will be eligible for inclusion if **ALL** the following criteria are respected:

- Men and women  $\geq$  18 years old.
- Patients diagnosed with Grade I – II symptomatic haemorrhoids (according to Goligher classification) confirmed by clinical and anoscopic or proctoscopic examination performed within 3 months before baseline.
- Patients able to do self-administration at home of the MD, for 30 days, to treat symptoms of haemorrhoids and anal irritation.
- Patient free from the following treatments for haemorrhoids for at least 4 weeks: laser treatments for haemorrhoids, steroid or non-steroidal anti-inflammatory drugs, analgesics, any anti-haemorrhoidal treatment, anticoagulants, and antiplatelet agents.
- Patients able to communicate adequately with the Investigator and understand the questionnaire.
- Patients able to understand and who can provide valid informed consent to the trial.

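### The report claims efficacy in anal irritation and a significant fall in four named symptoms, but only scale totals were tested and no item result is given

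*Combined protocol and SAP*

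**What the plan says.** Protocol section 2.3 sets the aim of evaluating the device in "relieving symptomatology of haemorrhoidal disease and anal irritation in adult patients" with Grade I–II haemorrhoids. The report's Summary repeats the pairing in its Conclusions ("effective in improving quality of life and reducing the symptoms associated with hemorrhoidal disease and anal irritation in adult patients"). Its Discussion goes down to single symptoms: "The significant reduction in pain, itching, burning, and swelling highlights the product's efficacy".

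On who was studied, section 3.3.1 requires "Patients diagnosed with Grade I – II symptomatic haemorrhoids (according to Goligher classification) confirmed by clinical and anoscopic or proctoscopic examination". Irritation is named in one inclusion criterion, as a purpose of use: "Patients able to do self-administration at home of the MD, for 30 days, to treat symptoms of haemorrhoids and anal irritation".

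On what was measured, Annex 3 introduces the SHS-HD as dealing with "how your symptoms caused by hemorrhoids affect your daily life"; its fourth item asks about general well-being. The HSS grades prolapse, number of columns, position relative to the dentate line, and bleeding. HDSS item 2 asks "How often do you feel itching or discomfort of the anus". The schedule of assessments has all three scales completed at Visit 1 and Visit 2.

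On what was analysed, the Statistical Methods in report section 9 test the totals of the three scales. Tables 5 to 7.3 report totals only. Protocol section 4.3.2 plans no item-level analysis.

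**The concern.** A claim about a particular symptom needs a result for that symptom. The report has significant falls in three sum scores and then writes as if the components had been shown to fall. A sum of five items can fall because of some of them while others stay put.

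At stake is a product claim. The protocol says that post-marketing follow-up results go to the Notified Body, and the instructions for use list relief of haemorrhoids, of perianal itching and burning, and of sensitivity to anal irritation as separate points. A reader of the Conclusions would take the second and third as tested in this trial.

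**Working it through.** **Step 1. Reproduce the reported HDSS result.** Table 6 gives a mean difference (Visit 1 minus Visit 2) of 2.92 with SD 2.51, n = 50.

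- t = 2.92 / (2.51/√50) = 2.92 / 0.355 = 8.23. Table 6.1 reports 8.21; rounding of the inputs explains the gap.
- 95% CI = 2.92 ± 2.01 × 0.355 = 2.21 to 3.63, as in Table 6.

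The result for the total is consistent with itself. The sample size was set on the SHS-HD total and does not bear on this point.

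**Step 2. Match each claimed symptom to what was asked and reported.**

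| Claimed symptom | Closest question | Separate result reported |
|---|---|---|
| Anal irritation, itching | HDSS item 2 (itching or discomfort) | None |
| Pain | HDSS item 1 | None |
| Swelling | HDSS item 5 (swelling and prolapse asked together) | None |
| Burning | No item in any of the three scales | None possible |

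**Step 3. Ask what the HDSS total says about item 2.** Five equally scaled items make item 2 one fifth, or 20%, of the range. The total means are 10.12 at Visit 1 and 7.20 at Visit 2. Write a1 and a2 for the unknown means of item 2 at the two visits.

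- *Items coded 0–4* (the other four may sum to 0–16). Any a1 from 0 to 4 leaves 6.12 to 10.12 for the other items, and any a2 from 0 to 4 leaves 3.20 to 7.20. Both are allowed, so a1 − a2 can be anything from −4.0 to +4.0.
- *Items coded 1–5* (the other four sum to 4–20). Any a1 from 1 to 5 leaves 5.12 to 9.12, which is allowed. At Visit 2 the other four need at least 4, so a2 is at most 7.20 − 4 = 3.20. Then a1 − a2 runs from 1 − 3.20 = −2.2 to 5 − 1 = +4.0.

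The observed range of totals does not rule out zero change either. Every HDSS total in Table 6 lies between 5 and 19. With 1–5 coding, an answer of 1 to item 2 at both visits leaves 4 to 18 for the other four, within 4–20. With 0–4 coding, an answer of 3 at both visits leaves 2 to 16, within 0–16. So item 2 could have been unchanged in every patient.

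An equal share of the fall would be 2.92/5 = 0.58 points for item 2, but nothing in the documents supports equal sharing.

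**Step 4. Check the coding.** Section 3.5.1 gives items scored 0 to 4 and a total of 0 to 20. Table 6 shows a minimum of 5.00 at both visits and a Visit 2 lower quartile of 5.00. Five is the floor if items were coded 1–5. This suggests a different coding without proving it, and it must be settled before any item result is read.

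**The case against.** The strongest reply is that irritation is not a second indication here. The Background lists perianal irritation and pruritus among the accompaniments of prolapsed internal haemorrhoids, the synopsis names pruritus as a manifestation, and both objective and conclusion are confined to adults with Grade I–II haemorrhoids. SHS-HD item 1, on overall severity of haemorrhoid symptoms, could also absorb itching. This reading is fair. It means a reader should not infer that half of the objective lacks a population and an endpoint: the primary objective is quality of life, and the population is defined. But if irritation is only part of haemorrhoidal symptoms, naming it separately adds nothing. If it is named, a result is needed.

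A reader might also infer that irritation was never measured at baseline or never analysed. The documents do not support that. HDSS item 2 is scheduled at Visit 1 and enters a total that was tested. What is missing is an eligibility requirement, a reported baseline count and a separate result.

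Finally, the bounds in Step 3 are logical limits that would apply to an item in any sum score, and are not evidence that item 2 failed to improve. That is right. They show only that the total cannot stand in for the item.

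**Conclusion.** The Discussion and Conclusions state effects on anal irritation, pain, itching, burning and swelling for which the report gives no separate result. For burning, no scale contains a question. For itching or discomfort, the data exist but are not shown, and the reported totals are compatible with improvement, no change or worsening.

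This is a reporting overclaim. It does not affect the results for the SHS-HD, HDSS or HSS totals, and it does not show that the device fails to relieve irritation. The conclusion rests on the annexed questionnaires being those used and on no item-level output existing outside these documents. The numerical bounds use only the published HDSS means and range, under the two plausible codings.

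**What to change.** The simplest change is to remove anal irritation and the named-symptom sentence from the report's Discussion and Conclusions, and to state the findings as changes in the three totals. The protocol objective should be left as it stands, because it records what was planned.

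If the sponsor wishes to keep a statement on irritation, first confirm how HDSS items were coded. Then add one table, labelled post hoc, with:

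- the distribution of item 2 at Visit 1 and Visit 2;
- the number of patients above 'never' at baseline;
- the paired change with a 95% CI in all 50 patients.

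Any subset with the symptom at baseline should be descriptive only. Selecting on a raised baseline invites regression to the mean, and there is no control arm to gauge it. The table should also note that the response options reach back to less than once a month, while the schedule places Visit 2 at day 14. Pain and swelling would need the same treatment from items 1 and 5, or should come out.

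Burning should be removed in either case.

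The cost is a wording change, or one table from questionnaires already completed. The downside is a narrower claim if item 2 did not change.
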